8.2.3.1 Intensity

Intensity will be recorded for each reported AE. The following definitions of intensity are to be used:

Mild: Awareness of symptoms or signs, but easily tolerated (acceptable)

Moderate: Enough discomfort to interfere with usual activity (disturbing)

Severe: Incapacity to work or to do usual activity (unacceptable)

If the intensity changes within one day, the maximum intensity of the AE during that day shall be recorded.

8.2.3.2 Causal relationship and seriousness

Each AE, serious as well as non-serious, shall be assessed by the Investigator for causal relationship with the study product and its use (the injection procedure) and for seriousness (Yes or No) of the event.

A two-point scale (Yes or No response) shall be used for the causality assessments. The Investigators shall be asked to indicate a response to each of the following questions in the eCRF:

- “Do you consider that there is a reasonable possibility that the event may have been caused by the study product?”, and
- “Do you consider that there is a reasonable possibility that the event may have been caused by the study product injection procedure?”

If any of these questions is answered Yes, the AE is considered related.

Each AE will also be assessed for causal relationship and seriousness by the Sponsor, in order to fulfil regulatory requirements.

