3.1.2 Secondary efficacy objectives and endpoints

3.1.3 Safety objective

The safety objective is:

- To evaluate the safety of Restylane Kysse, Defyne, and Refyne by assessment of AEs by the Treating Investigator throughout the study period.

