5.5 Withdrawal of subjects

An Investigator may decide to discontinue a subject from the clinical study for safety reasons.

Although the importance of completing the entire clinical study should be explained to the subject by the clinical study personnel, any subject is free to discontinue participation in this clinical study at any time and for whatever reason, specified or unspecified, and without any prejudice. No constraints are to be imposed on the subject, and when appropriate, a subject may be treated with other conventional therapy when clinically indicated.

When a subject does not complete the clinical study, he/she will be fully assessed, if such assessment is possible. The procedures designated for the Early Termination (ET) visit should be completed for all subjects discontinuing the clinical study and the appropriate eCRF should be completed.

[figure not shown]
All discontinuations and the reason for discontinuation are to be documented by the Investigator.

For discontinuation due to an AE, the Adverse Event form is to be completed. The Investigator should also ensure that the subject receives suitable therapy for the AE.

Pregnancies occurring during the screening period are considered as screening failures; they should be recorded as such in the eCRF and no pregnancy form is to be completed.

In case of a pregnancy occurring after the baseline visit, the procedures described in Section 8.2.8 should be followed. The subject may remain in the study, but no invasive procedure should be conducted.

The Sponsor may also decide to prematurely terminate or suspend a subject's participation in the clinical study.

If an AE which, according to the Investigator's assessment, is related to the use of any of the study products and is still ongoing at the time of the withdrawal, the Investigator shall follow-up the subject until the AE resolves, is assessed by the Investigator to be "chronic" or "stable" or for at least 3 months.

6. Study Product

The term "study product" refers to Restylane Kysse, Restylane Defyne and Restylane Refyne.

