8.2.3 Recording instructions

Each subject should be questioned about AEs at each study visit following signing of informed consent. The question asked should be: "Since your last clinical visit; have you had any health problems?". Information on AEs can also be obtained from signs and symptoms detected during each examination or from a laboratory test, observations made by the study site personnel, subject diaries, or spontaneous reports from the subjects or their relatives.

Exceptions from AE reporting are normal fluctuations in pre-existing diseases. However, pre-existing illnesses that deteriorate shall be reported as AEs.

When an AE is related to a device deficiency (refer to Section 8.3), including technical device malfunction, the AE shall be recorded on the AE form/module in the eCRF and the technical complaint shall be reported separately on the clinical study complaint form.

Investigators, or other study site personnel, shall record all AEs in the eCRF, including:

- a) Event term (recorded in standard medical terminology and avoiding abbreviations)
- b) Affected area
- c) Start date (first day with symptoms)
- d) Stop date (last day with symptoms)
- e) Intensity (mild, moderate, or severe according to definition in Section 8.2.3.1)
- f) Seriousness (serious or not serious, according to definition in Section 8.2.3.2)
- g) Causal relationship to study product or study product injection procedure (yes or no)
- h) Action taken (none, medication treatment, non-pharmacological treatment, or other procedures/tests, subject withdrawn)
- i) Outcome of the AE (ongoing, recovered, recovered with sequelae, death, chronic/stable, not recovered at the end of the study)

The AE form/module in the eCRF must be signed and dated by the Investigator.

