10.5 Safety analysis

AEs will be coded according to MedDRA and summarized by system organ class (SOC), preferred term (PT).

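### Causality is asked once for all three fillers together, so in co-treated subjects the investigator's judgment names no product

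*Protocol*

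**What the plan says.** Protocol section 3.1.3 sets the safety objective for three named products: "To evaluate the safety of Restylane Kysse, Defyne, and Refyne by assessment of AEs by the Treating Investigator throughout the study period". The opening of section 6 says that the term study product "refers to Restylane Kysse, Restylane Defyne and Restylane Refyne".

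Section 8.2.3.2 gives two causality questions in full. The first is "Do you consider that there is a reasonable possibility that the event may have been caused by the study product". The second is "Do you consider that there is a reasonable possibility that the event may have been caused by the study product injection procedure". A Yes to either makes the event related. The list of recorded items in section 8.2.3 has the matching entry, "Causal relationship to study product or study product injection procedure (yes or no", and separately an entry for "Affected area". No listed item names a product.

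Section 4.1 puts Kysse in the lips for everyone. Group A (20 subjects) gets nothing else. Group B (30 to 40 subjects) also gets Defyne, Refyne or both in the facial wrinkles and folds. Section 6.6.6 has the administration details entered in the eCRF, and section 6.5 requires dispensing logs that link product name and batch to the subject.

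The visible text of section 10.5 is one sentence: "AEs will be coded according to MedDRA and summarized by system organ class (SOC), preferred term (PT".

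**The concern.** An objective that names three products calls for data that can be read product by product. The causality answer is the one place where the investigator's clinical judgment on cause is recorded, and it is recorded for the three fillers as a block. Most subjects receive more than one of them.

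What is at stake is how far the safety objective can be met for each filler, above all for Defyne and Refyne, which are never given without Kysse. The primary endpoint, the subject-rated GAIS at 8 weeks, is not affected.

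**Working it through.** The plan states no figure on this point to reproduce. The check is a small count followed by a comparison of the sections.

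**Share of subjects affected** (inputs from protocol section 4.1)

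- Group totals: 20 + 30 = 50 and 20 + 40 = 60, which agrees with the stated 50 to 60 treated.
- Co-treated share: 30/50 = 60%, and 40/60 = 66.7%.
- In the 20 Group A subjects only one filler is a candidate, so the collective question does no harm there.

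**What the other records can recover in Group B**

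| Type of related event | Records that help | Product identified? |
|---|---|---|
| Confined to the lips | Affected area; only Kysse is placed there | Yes, by inference |
| Confined to the folds, one fold filler used | Affected area plus administration record | Yes, by inference |
| Confined to the folds, Defyne and Refyne both used | Affected area does not separate them; depends on whether the administration record shows which filler went where | Not reliably |
| Spanning lips and folds | Affected area covers both | No |
| Systemic | Affected area carries no information | No |

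Two features of the protocol bear on the last three rows.

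- Section 2.3 places the Defyne and Refyne treatment in folds around the lips. Section 8.2.9 anticipates bruising, swelling, pain and tenderness, which can spread from one area to the next.
- Timing gives little help. Section 4.1 has subjects injected at Day 1 and allows touch-up at Week 4 for every product used initially, so onset relative to injection need not distinguish the fillers.

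**Other possible sources of a product name**

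- Section 8.2.5 lists the name of the study product in the minimum content of an initial SAE report. This covers serious events only. Since the term is collective, the entry need not express which filler is suspected.
- Section 8.2.3.2 adds a causality assessment by the sponsor, but does not say that it is made per product.
- The SAP supplied describes a different study: randomized, about 280 subjects, Kysse against a control. Its adverse event listing by affected treatment area is therefore not evidence for or against this study's plan.

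**The case against.** The strongest reply is that the data already support attribution for most of what will be seen. Fillers are separated by site, each event carries an area, and injections are recorded by subject. An investigator answering per product for a local event would mostly be reading off its location. For a systemic event after injection of several fillers, a per-product answer records an opinion and does not separate the exposures. This stands, and it limits the point to the last three rows of the table.

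A reader might go further and infer that related events in Group B cannot be assigned to a product at all. The documents do not support that: lip events, and fold events after a single fold filler, can be assigned indirectly.

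A reader might also infer that lip and fold events will be pooled into one related-event rate over all treated subjects, diluting any signal for Defyne or Refyne. That is not established either. Sections 10.1 and 10.4 are blacked out, most of section 6.6 is not visible, and the one visible sentence of section 10.5 does not mention intensity, duration or onset, although section 3.1.4 makes them safety endpoints. That sentence cannot be taken as the whole safety analysis, so a split by group, area or product may exist in text that cannot be seen.

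Finally, the study is open-label and descriptive, and its objective promises no product-specific rates. This lowers the priority but does not remove the mismatch. The causality questions are unredacted, complete, and not asked per product.

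**Conclusion.** The point holds in a limited form. The investigator's causality judgment is recorded for the three fillers collectively, while the objective names them one by one. This concerns the 60% to 67% of subjects planned for Group B. Within that group the real loss is confined to events crossing the lip-fold border, systemic events, and Defyne versus Refyne where both were given.

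The number of events in those categories cannot be estimated. The documents give neither expected event rates nor the split of Group B between Defyne, Refyne and both. The conclusion assumes that the eCRF, which was not supplied, follows the wording of sections 8.2.3 and 8.2.3.2 and has no additional per-product field.

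This is a worthwhile, inexpensive improvement to the safety data. It is not a flaw that undermines the study.

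**What to change.** In section 8.2.3.2, item (g) of section 8.2.3 and the eCRF, ask the product-causality question separately for each filler the subject actually received, with a yes/no answer each. Keep the injection-procedure question as it is. The judgment is best captured when the event is assessed, so this part should be in place before enrolment.

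In section 10.5, unless the redacted statistical text already does so:

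- present adverse events by Group A and Group B and by affected area;
- present related events per product, with the subjects injected with that product as the denominator.

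The affected area, administration records and dispensing logs needed for the groups, areas and denominators are already collected.

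The cost is one extra yes/no item per event for a subject given two fillers and two for a subject given three, plus a few tables. No visit or assessment is added. The denominators for Defyne and Refyne will be small, so their rates will be imprecise. Some events, chiefly near the lip border, will be marked as related to more than one filler. The table notes should say that such events are counted under each product marked, so that product counts are not added together.

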8.2.4 Reporting of adverse events

Adverse event reporting on each subject shall start at Visit 1 (Screening). The reporting shall continue during each follow-up visit (including telephone contacts and extra visits between planned visits) until the last scheduled visit in the study, Visit 6 (Follow-up at 8 weeks after last treatment).

All AEs, non-serious as well as serious, are to be reported as an AE in the eCRF.

8.2.5 Reporting of serious adverse events

The Investigator shall report any SAE to the Sponsor **immediately but not later than 24 hours of awareness of the event**. This initial report shall be submitted via the eCRF.

In case of difficulty to obtain all the required information within 24 hours, an initial report can be submitted, with the following information as a minimum, irrespective of whether some of it is regarded as preliminary:

- Subject identification (age, gender, initials, subject number)
- Adverse event description
- Date when AE occurred
- Name of PI
- Name of study product

Follow-up information and data missing in the initial SAE reporting shall be gathered as soon as possible and reported to the Sponsor immediately but not later than 24 hours of awareness of the new data. Complete and adequate information on each SAE is required. All attempts to obtain this information, including dates for follow-up activities, must be documented by the Investigator.

Supporting documentation to be provided with the SAE report:

- Concomitant therapies form/list
- AE form/list

- Medical history form/list
- Any other relevant supporting documentation (e.g. hospital notes, death certificate, autopsy reports etc.)

E-mail for SAE reporting:

[REDACTED]

For non-urgent complementary information not possible to send by e-mail or fax, please use surface mail.

Surface mail for providing complementary information:

Q-Med AB

[REDACTED]

The SAE form must be signed and dated by the Investigator. If the initial 24-hour SAE report does not contain full information or if it is made without using the SAE form the fully completed and signed SAE form shall be e-mailed or faxed to the Sponsor. A copy of the fully completed SAE form shall be kept at the site.

In addition, the PI shall report SAEs to the responsible IEC without undue delay. The PI is responsible for checking what reporting procedures are applicable for his/her IEC regarding SAEs and final report of the outcome of the study and to comply with such reporting procedures during the study period.

The Sponsor is responsible for reporting to the RA, if applicable and according to national regulations.

8.2.6 Follow-up of unresolved events ongoing at termination of the study

All serious as well as non-serious AEs with a causal relationship to the study product or treatment procedure and ongoing at study end, shall be followed up after the subject's participation in the study is over. Such events shall be followed up after the last study visit until resolved, assessed as chronic or stable, or for three months. Final outcome after the end of the study shall be reported on AE follow-up form.

8.2.7 Reporting and follow-up of events occurring after subject termination of the study

All AEs with a causal relationship to the study products or treatment procedure that the Investigator becomes aware of, serious as well as non-serious, with onset after the study termination (subject's last study visit) shall be reported to the Sponsor. The report should as a minimum include the information described in Section 8.2.3. The report can be sent via fax or e-mail according to contact details specified in Section 8.2.5. The events shall thereafter be followed up until resolved or considered chronic or stable, or for at least three months. Final outcomes shall be reported.

8.2.8 Pregnancy

Pregnancy itself is not regarded as an AE.

If there is a pregnancy during the study period, the subject must be withdrawn from any following study treatment but should continue to be followed within the study and the outcome of pregnancy must be reported even if the delivery occurs after study completion.

A pregnancy confirmed during the study period must be reported by the Investigator on a pregnancy report form immediately upon acknowledgement be submitted to the Sponsor according to contact details specified in Section 8.2.5. The report can be prospective or retrospective. Follow-up shall be conducted to obtain outcome information on all prospective reports.

Cases that led to fetal distress, fetal death or a congenital abnormality or birth defect are to be regarded as SAEs and shall be reported on the exposure in utero report form to the Sponsor immediately but no later than 24 hours after the Investigators awareness. These events shall be handled as SAEs during data processing. Other complications during the pregnancy that are related to the pregnant woman and fulfils any serious criteria, such as pre-eclampsia requiring hospitalization, shall be reported and handled as SAEs. Elective abortions without complications shall not be reported as AEs.

8.2.9 Anticipated adverse events

Injection related AEs such as bruising, erythema, itching, swelling, pain and tenderness are anticipated. Information regarding anticipated AEs for Restylane Kysse, Restylane Defyne, and Restylane Refyne are included in the IFUs (co-packed with product).

8.3 Device deficiencies

8.3.1 Definition of a device deficiency

A device deficiency is defined as an inadequacy of a medical device with respect to its identity, quality, durability, reliability, safety⁴, or performance.

Note: Device deficiencies include malfunctions, use errors, and inadequate labelling.

8.3.2 Recording instructions

When a device deficiency is discovered, Part A of the clinical study complaint form shall be completed by the Investigator. The type of complaint shall be described and injury to the subject or user or unintended exposure to study product shall be reported as applicable. If an injury has occurred, an AE or an SAE form shall be completed as applicable (refer to Section 8.2.5). If no SAE was experienced as a result of the device deficiency the Investigator shall assess whether or not the device deficiency could have led to an SAE if:

- Suitable action had not been taken,
- Intervention had not been made or,
- Circumstances had been less fortunate

⁴ Inadequacy of device safety refers to properties of the device which could have or have led to an AE.

In Part B of the clinical study complaint form the Sponsor will make the same assessment.

8.3.3 Reporting of device deficiencies

The Investigator shall send the completed clinical study complaint form to the Sponsor.

[REDACTED]
[REDACTED]
[REDACTED]

[REDACTED]
[REDACTED]

A device deficiency that led to a SAE and any device deficiency that could have led to a SAE shall be reported to the Sponsor within 24 hours after the Investigator's awareness (for contact information, see Section 8.2.5).

If the Investigator or the Sponsor assesses that the device deficiency could have led to a SAE the Sponsor is responsible for reporting the device deficiency to RA and the PI is responsible for reporting it to the IEC.

The deficient study product shall be kept by the study site until the Sponsor has confirmed whether the product shall be returned to Sponsor for further study or if it can be destroyed at the study site.

9. Data Handling and Management

9.1 Data management

Data management based on GCP refers to the activities defined to achieve safe routines to enter clinical data information into a database, efficiently and avoiding errors. The data management routine includes procedures for database set-up and management, data entry and verification, data validation, and documentation of the performed activities including information of discrepancies in the process. The data management process will be described in detail in the data management plan (DMP).

The database, the data entry screens and program will be designed in accordance with the CSP and the CRF template. Data validation will be performed by computerized logical checks and manual review. Drugs and events will be coded in accordance with World Health Organization (WHO) Drug and medical dictionary for regulatory activities (MedDRA) dictionaries as specified in the DMP. Safety data (SAE and if applicable AE of special interest) in the clinical database will be reconciled against the data in the safety database.

When all efforts have been made to ensure that the data recorded in the eCRFs and entered in the database is as correct and complete as possible, the clinical database will be locked. Study data will be transferred to SAS datasets, which thereafter will be write-protected. Statistical analyses will be generated in SAS using data from the locked datasets.

9.2 Electronic case report forms

An electronic data capture application, compliant with regulatory requirements for software validation will be used to collect, modify, maintain, archive, retrieve, and transmit study data. An eCRF is required and shall be completed electronically for each screened subject (screening visit) and included subjects (subsequent visits).

The eCRF includes password protection and internal quality checks, such as automatic range checks, to identify data that appear inconsistent, incomplete, or inaccurate. Study data shall be entered directly from the source documents, which are to be defined at each site before inclusion of the first subject.

Authorized study site personnel designated by the PI shall complete data collection. Appropriate training and security measures shall be completed with all authorized investigation site personnel prior to the study being initiated and any data being entered into the system for any subject.

The study data is the sole property of the Sponsor and shall not be made available in any form to third parties, except for authorized representatives of appropriate RA, without written permission from the Sponsor. At the end of the study, electronic data are kept at the Sponsor and a copy (provided by the vendor) at the study site as part of the Investigator file.

Any delegation of collection of data shall be specified and recorded.

9.2.1 Data entry

All data shall be entered in English. The eCRFs should always reflect the latest observations on the subjects participating in the study. Therefore, the eCRFs shall be completed as soon as possible during or after the subject's visit. The subject's identity must always remain confidential, i.e. the name and address of the subjects must not be registered in the eCRFs or in the database. The Investigator must verify that all data entries in the eCRFs are accurate and correct. If some assessments are not done, or if certain information is not available, not applicable or unknown, the Investigator shall indicate this in the eCRF. The Investigator shall electronically sign off the study data. By signing, the Investigator takes responsibility for the accuracy, completeness, and legibility of the data reported to the Sponsor in the eCRF.

